## **6.2. Study Visits and Procedures**

### *a. Screening Visits and Procedures*

Patients will be screened at the ED for suitability before consent is taken. Prior to recruitment, the patient will first be stabilized and assessed by their primary physician. Recruitment will only take place after an initial ECG has been done, and the results of the initial serum troponin has been released, as both the ECG results and serum troponin results are required to assess the patient's risk for subsequent MACE.

### *b. Study Visits and Procedures*

Patients enrolled will be stratified by gender and randomized 1:1 into either the intervention arm (CPC) or control arm (usual care). For patients with low risk chest pain, an initial electrocardiogram and serial troponin will be done as part of standard care. Serial serum troponin tests will also be taken at the discretion of the attending physician. Further tests to evaluate the patient's cardiac function such as stress tests (e.g. stress treadmill electrocardiogram, stress myocardial perfusion imaging, etc.) or a computed tomography of the coronary arteries (CTCA) may either be arranged as part of the patient's ED observation unit stay or outpatient as part of standard care. For research purposes, those under the intervention arm will receive the chest pain choice visual aid prior to discussion with their primary physician regarding disposition.

### *c. Post Study Follow up and Procedures*

The subjects will then be followed up at 60 days for 30-day and 60-day MACE, repeat ED attendance, and subsequent cardiac testing performed via a review of electronic medical records or contact via telephone if electronic medical records are not available. No other study visits are required.

### *d. Discontinuation Visit and Procedures*

Subjects may withdraw voluntarily from participation in the study at any time. Subjects may also withdraw voluntarily from receiving the study intervention for any reason. In these circumstances, patients will be treated with usual care, and follow-up will be as clinically indicated, as decided by their attending physician.

## **7. SAFETY MEASUREMENTS**

### **7.1. Definitions**

Serious adverse events are defined as either 30-day or 60-day MACE. If there is an increase in 30-day or 60-day MACE amongst subjects in the intervention arm during interim analysis at 50% of our recruitment target, the PI will be responsible for reporting this to the DSRB.

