### **2.3. Secondary Objectives**

1. To determine if the CPC can improve patient knowledge and increase patient involvement in shared decision-making
2. To evaluate the impact on the incidence of MACE, ED re-attendances and downstream cardiac evaluation (either stress tests or computed tomography of the coronary arteries) at 30-days and 60-days with the implementation of CPC

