The patients in both groups will be assessed regarding their pre- and post-consultation knowledge as well as satisfaction during this visit by standardized questionnaires. The patients will be followed up at 60 days to find out if they had MACE, ED re-attendances, as well as whether further tests for cardiac evaluation were done. This will be done via a review of their electronic medical records or via telephone contact if electronic medical records are not available. A MACE is defined as all-cause mortality, myocardial infarction or coronary revascularisation.

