### **7.3. Safety Monitoring Plan**

The PI and study team will perform data and safety monitoring. The data will be reviewed on a quarterly basis and both adverse and serious adverse events such as 30- and 60-day major adverse cardiac events will be monitored. The principal investigator will review the study data on a quarterly basis for completeness. Data integrity will be assured by the means of doing spot checks on the data collected and comparison with the patient's electronic records. The study will be stopped based on safety if it is shown that there is an increase in 30- or 60-day MACE for patients in the intervention arm. The dissemination of data and safety information will be done by the principal investigator via face-to-face contact and e-mail if necessary.

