### **9.2. Statistical and Analytical Plans**

Intention-to-treat analysis will be carried out; proportions will be evaluated using chi-square tests, non-parametric variables with Mann-Whitney *U* and parametric variables with Student's *t* tests as appropriate.

An interim analysis will be done when 50% of recruitment has been reached to check for incidence of adverse outcomes such as 30-day or 60-day MACE. If there is a significant increase in 30-day or 60-day MACE in the intervention arm as compared to the control arm, the study will be stopped.

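### Section 7.1 limits serious adverse events to MACE, so non-fatal serious events outside MACE have no definition, no named place in the 60-day review and no planned comparison by arm

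*Combined protocol and SAP*

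**What the plan says.** Section 7.1 gives a closed definition: "Serious adverse events are defined as either 30-day or 60-day MACE". Section 6 closes the inner term as well: "A MACE is defined as all-cause mortality, myocardial infarction or coronary revascularisation".

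Section 7.3 is wider. At the quarterly review, "both adverse and serious adverse events such as 30- and 60-day major adverse cardiac events will be monitored". There MACE illustrates a larger class, and no section defines the rest of that class. Section 9.2 has the interim analysis "check for incidence of adverse outcomes such as 30-day or 60-day MACE", which is also open-ended.

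The comparisons that lead to action return to MACE alone. Section 9.2 acts "If there is a significant increase in 30-day or 60-day MACE in the intervention arm as compared to the control arm", and section 7.3 says "The study will be stopped based on safety if it is shown that there is an increase in 30- or 60-day MACE".

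Under section 6.2c, subjects are "followed up at 60 days for 30-day and 60-day MACE, repeat ED attendance, and subsequent cardiac testing performed". The matching secondary objective in section 2.3 is "To evaluate the impact on the incidence of MACE, ED re-attendances and downstream cardiac evaluation", at 30 and 60 days.

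**The concern.** The intervention is expected to send more patients home. Section 1.2a asks whether it can do so safely, section 2.4a lists a safe reduction in admissions as a benefit, and section 2.4b names delayed testing and delayed definitive management as the risk.

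Harm from delay need not be fatal, and it need not be an infarction or end in revascularisation. A subject discharged with low-risk chest pain may be admitted days later with a different, life-threatening cause of that pain and survive. Under section 7.1 this is not a serious adverse event. At most it appears as one ED re-attendance, indistinguishable in the protocol text from a return for a trivial reason. If such events differed between arms, no planned table would show it as a difference in serious harm, and the safety conclusion would rest on a very small number of MACE.

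**Working it through.** **Step 1. Trace each type of event through the plan.**

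| Event by day 60 | Serious under 7.1? | Named in the 6.2c review? | Planned comparison by arm? |
|---|---|---|---|
| Death, any cause | Yes, through MACE | Yes | Yes (2.3, 7.3, 9.2) |
| Non-fatal infarction or revascularisation | Yes | Yes | Yes |
| Return to the ED | No | Yes, as a count | Yes, as a secondary outcome (2.3), without cause or seriousness |
| Non-fatal life-threatening event outside MACE | No | No | None as a harm |
| Unplanned admission after discharge, outside MACE | No | No | None as a harm |

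The gap is the last two rows.

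**Step 2. Compare the scope of the sections.** Sections 7.1 and 7.3 both use the term serious adverse event. Section 7.1 makes it identical to MACE, while 7.3 uses MACE as an example of adverse and serious adverse events together. Section 9.2 speaks of adverse outcomes and never uses the defined term. The wording conflict is therefore between 7.1 and 7.3; 9.2 is only looser in scope.

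**Step 3. How much information MACE alone carries.** Inputs: 82 per arm (section 9.1); 200 enrolled, so 100 per arm at 1:1 (section 3.1); MACE risk 0.9% to 1.7% (section 1.2b). The risk is a 6-week figure. Applying it to day 60 and to both arms is an assumption.

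Expected events per arm = n × p. Chance that an arm has none = (1 − p)^n.

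| n per arm | Expected MACE per arm | Chance of none in an arm |
|---|---|---|
| 41 (half of 164, interim) | 41 × 0.009 = 0.37 to 41 × 0.017 = 0.70 | 69% to 50% |
| 82 | 82 × 0.009 = 0.74 to 82 × 0.017 = 1.39 | 0.991^82 = 48% to 0.983^82 = 25% |
| 100 | 0.90 to 1.70 | 40% to 18% |

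With 82 per arm and no events in the control arm, Fisher's exact two-sided p is 0.059 for five events in the intervention arm and 0.028 for six. Six is more than four times the highest expected count of 1.39.

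The plan states no expected number of serious events, so there is no figure of its own to reproduce. The sample size in section 9.1 concerns the primary outcome and does not bear on this point.

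**The case against.** A reader might infer that serious harm outside MACE is never counted, or is invisible to monitoring. The documents do not support that.

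- All-cause death is part of MACE, so every fatal harm is counted and compared.
- ED re-attendance is recorded for both arms and, as a proportion, falls under the chi-square tests of section 9.2. A harm that brings the patient back is counted, although not as a serious event.
- Section 7.3 promises quarterly monitoring of adverse events as well as serious ones. It can be read consistently with 7.1: serious means MACE, and other adverse events are monitored too.
- Section 7.2 requires reporting of unanticipated problems within 7 calendar days, and of all local deaths within 24 hours.
- The data collection form in Appendix 2 is not reproduced in the text reviewed and may record more than section 6.2c names.

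The first two points stand in full. On the third, the consistent reading leaves the wider class undefined, with no stated means of collection and no comparison by arm. The section 7.2 route requires an event to be unexpected, at least possibly related and suggestive of greater risk. That is a case-by-case judgement in an unblinded trial, and it produces no table by arm. The fifth point limits the claim to what the protocol text states.

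It is also fair to object that sparse MACE is a matter of sample size, and that a wider definition would still give a weak comparison. Suppose, purely for illustration, that 5% and 10% of subjects had a qualifying event. The documents give no such rate. With 82 per arm and two-sided 0.05, power is Φ{[0.05√82 − 1.96√(2 × 0.075 × 0.925)] / √(0.05 × 0.95 + 0.10 × 0.90)} = Φ(−0.75), about 23%. The same formula gives about 15% for 3% against 6% and 44% for 3% against 10%. The objection stands: the change improves what is described, not what can be proved.

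**Conclusion.** The point holds in a limited form. Section 7.1 is narrower than 7.3, and the two should be reconciled. Non-fatal serious events outside MACE have no definition, no named place in the 60-day review and no planned comparison by arm.

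The plan therefore supports its conclusion about safety with about 0.7 to 1.4 expected MACE per arm at 82 per arm. This rests on the 6-week risk holding to day 60 in both arms, and on the Appendix 2 form adding nothing beyond section 6.2c. No estimate is offered of how many non-MACE serious events would occur, because the documents give no basis for one.

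A reader might also infer that section 9.2 contradicts 7.1. It does not, because it uses a different term. The primary outcome is unaffected. This is a modest, inexpensive improvement to the safety reporting.

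**What to change.** 1. In section 7.1, define a serious adverse event as any death, life-threatening event or unplanned hospital admission up to day 60, with MACE reported as a subset.
2. In the same sentence, exclude the index ED visit, the index observation-unit (EDTU) stay and any admission planned at the index visit for cardiac testing. This exclusion is essential. Disposition is decided after randomisation, and the index stay is the primary outcome. Without the exclusion, a CPC effect of the size in section 9.1 would by itself give the control arm 20 percentage points more subjects with a serious event (about 0.20 × 82 = 16 subjects) and make CPC look safer by construction.
3. In section 6.2c, add unplanned hospital admission after the index visit, with diagnosis, to the items reviewed at 60 days.
4. In sections 7.3 and 9.2, state that these events are tabulated by arm at the quarterly review, the interim and the end, as descriptive safety data. Leave the MACE stopping text as it is.

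The cost is protocol wording, one extra field in a record review already planned, more event forms and higher serious-event counts. No visit is added.

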### **7.2. Collecting, Recording and Reporting of "Unanticipated Problems Involving Risk to Subjects or Others" – UPIRTSO events to the NHG Domain Specific Review Boards (DSRB)**

**UPIRTSO events** refers to problems, in general, to include any incident, experience, or outcome (including adverse events) that meets ALL of the following criteria:

#### **1. Unexpected**

In terms of nature, severity or frequency of the problem as described in the study documentation (eg: Protocol, Consent documents etc).

#### **2. Related or possibly related to participation in the research**

Possibly related means there is a reasonable possibility that the problem may have been caused by the procedures involved in the research; and

#### **3. Risk of harm**

Suggests that the research places participants or others at a greater risk of harm (including physical, psychological, economic, or social harm) than was previously known or recognized.

#### **Reporting Timeline for UPIRTSO Events to the NHG DSRB.**

1. Urgent Reporting: All problems involving local deaths, whether related or not, will be reported immediately – within 24 hours after first knowledge by the PI.
2. Expedited Reporting: All other problems will be reported as soon as possible but not later than 7 calendar days after first knowledge by the PI.

### **7.3. Safety Monitoring Plan**

The PI and study team will perform data and safety monitoring. The data will be reviewed on a quarterly basis and both adverse and serious adverse events such as 30- and 60-day major adverse cardiac events will be monitored. The principal investigator will review the study data on a quarterly basis for completeness. Data integrity will be assured by the means of doing spot checks on the data collected and comparison with the patient's electronic records. The study will be stopped based on safety if it is shown that there is an increase in 30- or 60-day MACE for patients in the intervention arm. The dissemination of data and safety information will be done by the principal investigator via face-to-face contact and e-mail if necessary.

## **7.4. Complaint Handling**

Complaints will be addressed by either the PI or one of the co-investigators. Contact details of the PI are given to the participants at time of consent taking as part of the consent process, so that complaints or inquiries can be made. If the data obtained is pertaining to an UPIRTSO event or adverse outcome, it will be reported to the NHG DSRB.

## **8. DATA ANALYSIS**

### **8.1. Data Quality Assurance**

The principal investigator will review the study data on a quarterly basis for completeness. Data integrity will be assured by the means of doing spot checks on the data collected and comparison with the patient's electronic records.

### **8.2. Data Entry and Storage**

All research data will be stored within the study site. Hardcopy data will be stored in designated locked cabinets in the PI's office that are accessible to authorized study personnel only. Electronic data will be stored on a secured computer that is password-protected. The databases will not contain subject identifiers and the data linking subject identifiers and the subject identification codes will be stored separately. When portable media (e.g. CD, USB drives etc.) are used to store the data, subject identifiers are stored separately. The study team including the PI and co-investigators will have access to the research data. The research data will be destroyed after it has been stored for a minimum of 6 years.

## **9. SAMPLE SIZE AND STATISTICAL METHODS**

### **9.1. Determination of Sample Size**

A sample size of 164 patients (82 in each arm) will provide 80% power to detect an absolute difference of 20% reduction in admissions to ED observation unit in the intervention arm between the 2 groups, with 2-sided alpha of 0.05.

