#### **b. Rationale for Study Population**

The target population is that of adults aged 21 years and above who present to ED with chest pain that is considered low risk based on the HEART score (HEART score 0-3). The HEART score is a validated scoring system for patients aged 21 years and above who present with

symptoms suggestive of Acute Coronary Syndromes. The HEART score assigns different points for various features in the patient's history, ECG features, age group, presence of risk factors, and initial troponin level, in order to generate a score that corresponds to a range of percentages for the risk of 6-week MACE. Patients with a HEART score of 0-3 correspond to a 6-week MACE risk of 0.9-1.7%. Since the risk of 6-week MACE is low in these patients, outpatient follow-up and cardiac testing for underlying coronary artery disease can be considered instead of ED observation unit admission. This is also in keeping with current institutional practices.

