**3. STUDY POPULATION**

**3.1. List the number of subjects to be enrolled.**

A total of 200 subjects will be enrolled at the National University Hospital Emergency Department. There are no restrictions based on race. The study excludes children as it is targeted at patients with low-risk chest pain in an adult emergency department.

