**3.4. Exclusion Criteria**

All subjects meeting any of the exclusion criteria at baseline will be excluded from participation:

- Have a HEART score of 4 or more

- Are not English-literate
- Have an elevated initial serum troponin
- Have an initial electrocardiogram that is suggestive of cardiac ischaemia (ST-segment depression or elevation, new onset left bundle branch block, T-wave inversions, etc.)
- Have known coronary artery disease
- Have a prior plan for cardiac intervention or admission
- Have barriers to outpatient follow-up
- Are prisoners
- Are pregnant
- Are hearing or visually impaired, or are otherwise unable to use the clinical decision aid
- Do not consent to participation in the study

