### **3.6. Subject Replacement**

Subjects who drop out will be replaced until the minimum number of 164 patients has been achieved.

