## **6. METHODS AND ASSESSMENTS**

This is a randomized controlled trial; involving patients aged 21 years and above with low risk chest pain. Patients enrolled will be stratified by gender and then randomized 1:1 into either the intervention arm (CPC) or control arm (usual care). Randomization will be done via an online randomization generator. Recruitment will take place from Sunday 0800 hours to Thursday 2359 hours as inpatient cardiac evaluation investigations such as stress tests and CTCA are only available during weekdays, hence limiting the utility of the ED observation unit on weekends. Those under the intervention arm will receive the Chest Pain Choice visual aid prior to discussion with their primary physician regarding disposition. Data will be collected regarding the patients' age, demographics, past medical history and co-morbidities, cardiovascular risk factors, current medications, variables regarding their current visit such as vital signs, symptoms, laboratory results and electrocardiogram results, treatment received at the emergency department, eventual disposition and downstream cardiac test results if any. In addition to this, patients will answer a questionnaire which will assess patient knowledge, perceptions regarding the information received during consultation, patient satisfaction, as well as the Trust in Physician scale (a tool that assesses interpersonal trust in a patient-physician relationship) and the Decisional Conflict scale (an established tool that assesses personal perceptions regarding decision-making). Please see the data collection form and the patients' questionnaires in Appendix 2.

After discussion between the patient and his/her attending physician, patients will either be discharged from the emergency department with or without outpatient tests to evaluate their cardiac function (e.g. stress tests, CTCA) and/or outpatient Cardiology appointment or admitted to the ED observation unit for further observation and serial troponin testing, whereby further investigations for cardiac evaluation (e.g. stress tests, CTCA) may or may not be done or planned, at the discretion of the attending physician. There is variability in what is considered standard care, as it is dependent on several factors such as the patient's social set-up, availability of inpatient cardiac evaluation, etc., and hence standard care will not be strictly defined.

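### Does the sample-size statement in 9.1 need changing because it gives no control admission rate and does not link 164 to the 200 to be enrolled?

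*Combined protocol and SAP*

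**What the plan says.** Section 9.1 is one sentence: "A sample size of 164 patients (82 in each arm) will provide 80% power to detect an absolute difference of 20% reduction in admissions", with the reduction in the intervention arm and a two-sided alpha of 0.05. No control or intervention admission rate is given there or elsewhere. Section 9.2 compares proportions by chi-square under intention to treat and does not mention a continuity correction.

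Three other places bear on the number. Section 3.1: "A total of 200 subjects will be enrolled". Section 3.6 replaces dropouts "until the minimum number of 164 patients has been achieved". Section 7.1 refers to an "interim analysis at 50% of our recruitment target", and section 9.2 repeats the 50% without saying of which total.

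The plan gives only indirect hints about the control rate:

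- Section 6 on usual care: "hence standard care will not be strictly defined".
- The rationale for the study population (section 1.2) says outpatient follow-up and testing may be considered in place of observation, and adds: "This is also in keeping with current institutional practices".
- Section 3.4 excludes patients who "Have a prior plan for cardiac intervention or admission".
- Section 6 restricts recruitment to Sunday to Thursday because weekday-only testing is described as "hence limiting the utility of the ED observation unit on weekends".
- The rationale for the study purpose (section 1.2) describes clinicians as cautious about discharging without testing, and some admissions to the unit as unnecessary.

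**The concern.** An absolute difference does not fix the power of a two-proportion comparison. The variance depends on where the two rates lie and is largest when they straddle 50%. Without the control rate, a reader cannot confirm that 82 per arm gives 80% power. For control rates strictly between 40% and 80% it gives less.

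The hints do not settle the rate. Existing use of outpatient follow-up and the exclusions suggest a lower one; the recruitment days and the description of cautious clinicians suggest a higher one. A low rate would also matter in another way. A 20-point drop halves admissions from 40%, removes two thirds of them from 30%, and cannot occur below 20%. A null result might then be hard to interpret.

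The two totals add to the doubt. Half of the recruitment target is 82 or 100 patients, depending on which total is meant, and the interim look can stop the trial.

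**Working it through.** **Inputs.** From 9.1: 82 per arm, difference d = 0.20, two-sided alpha 0.05 (z = 1.960), power 80% (z = 0.842). From section 5: 1:1 allocation. From 3.1: 200 in total, so 100 per arm. The control rate p1 is not in the documents, so it is varied, with p2 = p1 − 0.20 and m = (p1 + p2)/2.

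**Formulas** (pooled variance, uncorrected chi-square):

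- n per arm = [1.960·√(2m(1−m)) + 0.842·√(p1(1−p1) + p2(1−p2))]² / d²
- power = Φ{ [d·√n − 1.960·√(2m(1−m))] / √(p1(1−p1) + p2(1−p2)) }

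**Reproducing the plan's figure.** At 40% v 20%, m = 0.30. The terms are 1.960·√0.42 = 1.270 and 0.842·√0.40 = 0.532. Then (1.270 + 0.532)²/0.04 = 81.2, rounded up to 82 per arm, or 164 in total. By symmetry 80% v 60% gives the same. Power at 82 is Φ[(1.811 − 1.270)/0.632] = 80.4%.

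**Worst case.** Both variance terms peak at m = 0.50, that is 60% v 40%. There n = (1.386 + 0.583)²/0.04 = 96.9, so 97 per arm (194 in total). Power at 82 is Φ[(1.811 − 1.386)/0.693] = 73.0%. At 100 it is Φ[(2.000 − 1.386)/0.693] = 81.2%.

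| Control v intervention | Power, 82 per arm | Power, 100 per arm |
|---|---|---|
| 30% v 10% | 90.0% | 94.8% |
| 40% v 20% | 80.4% | 87.6% |
| 50% v 30% | 74.8% | 82.8% |
| 60% v 40% | 73.0% | 81.2% |
| 70% v 50% | 74.8% | 82.8% |
| 80% v 60% | 80.4% | 87.6% |

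Exact enumeration of the uncorrected test at 60% v 40% gives 73.4% with 82 per arm and 82.6% with 100. With a continuity correction, 100 per arm gives 78.7% there.

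**Loss that the 200 can absorb.** The worst case needs 194 analysed, so 6 of 200 (3%) can be lost before power falls below 80%. The primary outcome is disposition at the index visit, so it does not depend on the 60-day follow-up.

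**164 and 200.** 164/200 = 0.82, so 200 is what an 18% allowance on 164 would give. The plan does not state that allowance, but a minimum of 164 and a planned total of 200 are compatible.

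**Interim count.** At the six-week MACE risk of 0.9–1.7% quoted in section 1.2, 82 patients yield 0.7 to 1.4 expected events (82 × 0.009; 82 × 0.017) and 100 yield 0.9 to 1.7. The choice of total makes little difference to what that look can show.

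**The case for a change.** The strongest case for a change is that 9.1 makes its claim for 164, not 200, and that the claim holds for some control rates and fails for others. If recruitment stopped at the minimum and the rate were between 40% and 80%, power would be 73–80%. The 81.2% floor at 200 also has conditions: with a continuity-corrected test it becomes 78.7% (exact) at 60% v 40%. Nor does enrolling 200 help if usual-care admissions are already low. If the intervention halves admissions whatever the starting rate, 100 per arm gives 72.2% power at a control rate of 30% and 50.8% at 20%.

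The arithmetic stands, but it does not show an error. A planner assuming 60% v 40% would have obtained 97 per arm, so that scenario is not the one behind 82. Under the uncorrected formula, 82 points to 40% or 80%; under a corrected one, to about 34–35% or 85–86%. The constant halving is likewise an assumption from outside the plan, which specifies an absolute difference, and no section suggests a control rate of 20–30%. The trial will observe its own control rate, so readers of a null result can see whether a 20-point drop was attainable.

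What remains is that the assumed rates, their source and the reason for the margin above 164 are unwritten, as are the test variant and the total behind the 50% interim.

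**Conclusion.** No change to the plan is needed. The 80% in 9.1 is missing an input but is consistent with an ordinary calculation at 40% v 20% or 80% v 60%. Enrolling 200 as section 3.1 plans keeps power for a 20-point drop at 81.2% or more, whatever the control rate. This assumes an uncorrected chi-square test and at least 194 patients analysed in the worst case. The 73.0% applies only if the trial stopped at its minimum of 164 and the control rate were 60%.

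Sections 3.1 and 3.6 read naturally as a planned total and a minimum. The ambiguity in the interim count is 82 against 100 patients, with between 0.7 and 1.7 events expected. Writing the assumed rates, the reason for the margin and the interim total into the text would be good reporting. It would not alter enrolment, the primary test or the conclusion the trial can draw.
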